To assess bone quality and its effect on glenoid component loosening, we will take humeral head bone samples from all patients. These bone samples will be assessed by microCT to measure trabecular bone volume and connectivity as well as by mechanical testing. These data will be correlated with the trabecular bone volume of the glenoid defined by the pre-operative CT scans. In addition all bone quality measurements will be correlated with CT scan imaging of the glenoid at the time of surgery and at two year follow up.

In order to acquire consistent information on bone quality across the patients, a custom-made calibration phantom object will be located between the CT bed and the patient. The phantom object consists of three cylindrical rods, each with a known density of hydroxyapatite (0, 500, and 1,000 mgHA/cm³) embedded in a soft foam block. The grey-level of pixel from the rods will be used to calibrate the Hounsfield units and the corresponding bone density using custom-written software.

Patient Enrollment

The proposed clinical trial will randomly enroll patients indicated for standard of care anatomic total shoulder arthroplasty into one of the four treatment groups. Our goal is to have 20 subjects in each treatment group. To accomplish this goal, we will enroll up to 120 subjects to control for subject withdrawal after enrollment. To enroll at least 20 patients into each group, including Group 5 (SmartBase), new randomization envelopes will be generated that start at number 34. The distribution of patients into Groups 1 – 4 at the time that Group 5 was begun is:

Group 1: 8
Group 2: 7
Group 3: 7
Group 4: 10

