Thus, to reach 20 in each group, randomization envelopes will be created by the statistician, [name] (QHS), that have 12, 13, 13, 10 and 20 in Groups 1-5, respectively. The change in the odds of being assigned to a particular group will change from 25% previously, to 15 to 19% in Groups 1-4, and to 29% in Group 5. They will receive all pre-operative testing, intra-operative care, including all implants and post-operative care that is standard of care and specific to the surgeon and patient decisions for care. The only change for this clinical trial will be the type of surgical instruments used to place the glenoid guide pin, retention of the humeral head for bone quality analysis, placement of the beads and post-operative CT scanning. In all cases the surgeon is able and allowed to use their own surgical judgment to place the guide pin, prepare the bone and place the desired implant. In all cases, the surgeon can use any and all of the standard instruments or guides provided by the implant manufacturer as the surgeon would use if the patient were not enrolled in the study. If the surgeon chooses not to use the IRI or RTI technique then this would be noted as a deviation in plan, the reasons would be recorded and the patient would be excluded from the study without post-operative imaging and their pre-

operative and intra-operative data would be analyzed for the purpose of understanding the reasons for failure of the RTI technology to provide assistance for refinement of the technology.

Detailed Study Design:

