The study will randomly enroll 20 patients into each of the four treatment groups. We will have three surgeons with experience in shoulder arthroplasty; two of these have extensive experience with the IRI, RTI and SmartBones technology. All patients will have the standard of care indications for an anatomic total shoulder arthroplasty and will give informed consent for both the surgery and participation in this study. Consent and enrollment will be obtained by the surgeon during a routine office evaluation. All patients will get standard of care pre-operative x-rays and CT scan at least one week prior to surgery. Scan quality must meet study specific criteria and we expect that the scans will be performed at Cleveland Clinic. The pre-operative CT scan will be placed within our pre-operative planning software (OrthoVis, Custom Orthopaedic Solutions, Cleveland, OH). The surgeon will use this software to assess the glenoid bone pathology and select the optimal implant and placement of that implant.

Patients will have standard of care indications for primary anatomic arthroplasty and be able to get a pre-operative shoulder CT scan at the Cleveland Clinic or at an outside facility so long as the study includes the entire scapula and has 1mm or thinner sections. These parameters are required for accurate pre-operative planning as well as comparison with the post-operative CT scans. Standard of care pre- and post-operative x-rays (AP and axillary views) will also be obtained and can be performed at Cleveland Clinic or acquired from another health care facility. In all patients the standard x-rays and CT images provided by the radiology department will be available to the surgeon before and during the surgery.

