The IRI legs are placed virtually (manually) on a virtual SmartBone using an impact detection function in the 3D modeling software. From there the height of each IRI leg is measured and correlated to a number on the SmartBase. The SmartBase has hashes in 1/2 mm increments. The surgeon is then given a pre-operative plan that includes virtual photos of the IRI placement, the IRI leg lengths and numbers of each SmartBase height as calculated. Intra-operatively the IRI is assembled as normal and placed onto the SmartBase after each adjustable tab has been set to the appropriate height for each leg. The IRI is then used as normal.

Inclusion/Exclusion Criteria:

To be eligible for inclusion, a primary anatomic total shoulder arthroplasty must be indicated for the patient.

Outcome Measures:

By comparing computer generated pre-operative plan to post-operative component placement, we will be looking at three outcomes. First, we will compare the overall difference in component placement between the four treatment groups: SOC instrumentation, SOC instrumentation with SmartBone, intelligent reusable instrument with metal instead of plastic legs, and real time instrumentation. Secondly, we will compare the placement between the technologies within and between surgeons. All of the surgeons have extensive experience with anatomic total shoulder arthroplasty. Two of the surgeons have extensive experience with the pre-operative planning and the IRI and RTI technology. Thirdly, we will evaluate the difference in implant position between technologies based on severity of pathology. The quality of the bone core samples will be correlated to the possible loosening of the implants.

Sample Size:

We intend to have approximately 20 subjects in each of the 4 treatment groups. We expect to randomize up to 120 subjects to achieve 20-25 subjects in each treatment group.

Data Analysis

Average deviations from plan for the four treatment groups will be compared using mixed-effects ANOVA methods. Random effects will be included to account for correlation between observations introduced as a consequence of multiple observations of deviation being taken on a particular surgeon. If significant differences are found, multiple comparisons based on the ANOVA model will be made to compare each pair of groups, and will use Holm's step-down procedure to control the family-wise error rate of the tests.

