All analyses will be done using R software (version 3.0.0, Vienna, Austria). A significance level of 5% will be used for all testing.

Data Sheets

Clinical data collected pre- and post-operatively will be passive and active range of motion, manual muscle strength testing and shoulder functional scores, and co-morbidities, all of which are standard of care. Post-operative data will be collected at two years (\pm 2 months) after surgery. We will collect at the time of surgery the implant used, the time for surgical care glenoid exposure to end of pin placement. The implant used, the surgical instruments used and any comments from the surgeon as to the ease of use and accuracy of the instruments. Verbatim comments will be solicited and recorded by a research assistant attending all surgical procedures.

Pre-operative imaging data will include: glenoid version and inclination, estimated pre -morbid inclination, version and depth of glenoid bone loss using the glenoid vault model, preferred implant type inclination and version.

Post-operative implant placement to desired location will be defined for the location of the center peg of the implant in the superior/inferior (SI), anterior/posterior (AP) and medial/lateral (ML) dimension in millimeters and the trajectory of the center peg vs plan in version and inclination. The location of the implant in relation to the joint line as measured by the glenoid vault model will be measured in millimeters. Back side contact of the implant to the bone will be measured as a surface area in direct contact with the bone and any lucent lines around the implant pegs will be measured. Peg perforation and the location of the peg perforation will be recorded. The tantalum beads within each implant will be measured for translational or rotational movement.

Changes in implant position from post-operative CT scan (CT 1) vs the first post-operative CT scan (CT 2) will be correlated with back side seating, implant type, medialization of the joint line and peg perforation and severity of the post-operative pathology.

Study data will be collected and managed using REDCap (Research Electronic Data Capture). Tracking data will be stored in an Excel spreadsheet, which will exist only on password-protected computers or on restricted-access CCF servers. Only study personnel will have access to the data.

Adverse Events and Data Monitoring Committee (DMC):

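### The third outcome compares technologies by severity of pathology, but the analysis model has no severity term and no balancing of the new envelopes by severity is stated

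*Combined protocol and SAP*

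**What the plan says.** Outcome Measures lists three outcomes: the overall difference between technologies, the comparison within and between surgeons, and severity. The third reads: "Thirdly, we will evaluate the difference in implant position between technologies based on severity of pathology".

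Data Analysis compares average deviations from plan between groups by mixed-effects ANOVA, with random effects for surgeon and Holm-adjusted pairwise comparisons. It names no severity covariate and no interaction.

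Patient Enrollment sets the target ("Our goal is to have 20 subjects in each treatment group") and introduces the new list: "To enroll at least 20 patients into each group, including Group 5 (SmartBase), new randomization envelopes will be generated that start at number 34". It says the statistician will create envelopes "that have 12, 13, 13, 10 and 20 in Groups 1-5, respectively". It states nothing else about how the list is built: no strata, blocks or minimisation.

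The information needed is available before surgery. Detailed Study Design states: "All patients will get standard of care pre-operative x-rays and CT scan at least one week prior to surgery". It also has the surgeon assess the glenoid pathology in the planning software from that scan. Data Sheets lists the pre-operative imaging variables, among them glenoid version, inclination and estimated pre-morbid "version and depth of glenoid bone loss using the glenoid vault model".

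No section defines severity, sets a cut-off or gives the expected share of severe glenoids. The other use of the term, in Data Sheets, calls the pathology post-operative.

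**The concern.** An outcome that asks whether technologies differ by severity needs a defined severity measure, a model term that estimates the difference, and enough spread of severity within each group. The plan states none of the three. Without a severity term, the third outcome has no specified analysis, and the choice of measure and cut would be made after the deviations are known. If severe glenoids also fall unevenly across groups, the first outcome carries a chance imbalance that the stated model does not adjust for. The third outcome then rests on very few severe patients in some groups.

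**Working it through.** **The plan's own figures.** Envelopes per group are the target minus those already allocated: 20−8 = 12, 20−7 = 13, 20−7 = 13, 20−10 = 10, 20−0 = 20, which sum to 68. Divided by 68 these are 17.6%, 19.1%, 19.1%, 14.7% and 29.4%, in agreement with the stated change "to 15 to 19% in Groups 1-4, and to 29% in Group 5". The 8+7+7+10 = 32 patients already allocated can no longer be balanced.

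**Chance imbalance without stratification.** Inputs: five groups of 20 (Patient Enrollment) and m severe patients among 100 (assumed 20, 30 or 40). The expected number per group is m/5 = 4, 6 or 8, and half of that is h = 2, 3 or 4. The probability that every group has more than h is the coefficient of x^m in [Σ_{j>h} C(20,j) x^j]^5, divided by C(100,m). One minus this gives:

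- m = 20, some group with 2 or fewer: 0.71
- m = 30, some group with 3 or fewer: 0.39
- m = 40, some group with 4 or fewer: 0.17

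Simulation gives the same values to within about 0.01. The largest and smallest groups differ by 5 or more severe cases in 38%, 53% and about 60% of trials.

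**Dependence on the threshold.** With a fixed threshold (fewer than 3 severe in some group) and binomial counts, 1 − P(X≥3)^5 with X ~ Bin(20, p) is 0.69, 0.16 and 0.02 at p = 0.2, 0.3 and 0.4. The risk of a nearly empty severe cell is therefore large at a 20% share and negligible at 40%.

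**Effect of stratifying the remaining 68.** The ratio 12:13:13:10:20 has no common factor, so the exact block is all 68 envelopes. Blocks of 3:3:3:2:5 (16 envelopes) give 18.75%, 18.75%, 18.75%, 12.5% and 31.25%, close to the intended shares. With the first 32 left as they are, the half-or-less risk becomes:

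- 20% severe: 0.71 falls to 0.37
- 30% severe: 0.39 falls to 0.11
- 40% severe: 0.17 falls to 0.03

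The gain is limited at 20% because only 68 × 0.2 = 13.6 severe patients are expected, fewer than one block. With these blocks some group total misses 20 by three or more, in either direction, in roughly 15 to 27% of runs. Blocks of 2:2:2:2:3 miss by that much in 41 to 48%.

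**Scarcity.** The pairwise difference detectable with 80% power (two-sided 5%, before Holm) is (1.96+0.84) × √(1/n1+1/n2) in SD units:

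- 20 vs 20: 0.89
- 6 vs 6: 1.62
- 4 vs 4: 1.98
- 2 vs 6: 2.29

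Balance improves 2 vs 6 to 4 vs 4, which is a gain from 2.29 to 1.98 SD. A comparison restricted to severe cases stays weak either way. At a 20% share, the chance that some group has fewer than 5 severe cases is 0.99 unstratified, and still 0.97 if severe cases among the remaining 68 are spread in exact proportion.

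**The case against.** A reader might infer that the new envelopes ignore severity. The documents do not say so. They are silent on every feature of the list except its start and totals, so the supportable statement is that no balancing is stated.

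A reader might also infer that a group with few severe glenoids would leave the third outcome unanswerable. That does not follow. The outcome does not require a mild/severe split, and version and depth of bone loss are continuous measures. An interaction on the continuous scale uses all 20 patients per group and does not collapse because a group has three rather than six patients above a cut. It will still be imprecise at the severe end if few patients lie there.

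Further, the probabilities rest on a share and a cut that the plan does not give. Stratifying has a real cost in group totals, while Patient Enrollment aims for at least 20 per group. Severity is the third outcome, and surgeon ranks above it. The plan does not say when an envelope is opened relative to the CT being read. All of this stands, and it is why stratification is offered here only as an option.

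None of it removes the gap in the model. A named outcome has no term in the stated analysis although the baseline measure is collected.

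**Conclusion.** The point holds as a gap in the analysis plan with a plausible, not certain, design consequence. The third outcome has no definition of severity and no model term, and no balancing by severity is stated for the 68 new envelopes. If allocation is in fact unbalanced on severity, some group receives half or less of its expected severe cases in about 71%, 39% or 17% of trials at assumed shares of 20%, 30% or 40%. These figures assume 100 analysable patients in five groups of 20. Patients excluded without post-operative imaging, as the protocol provides when the IRI or RTI technique is abandoned, would lower the counts. The main comparison between groups remains valid under randomisation. Adjustment would protect it against chance imbalance to the extent that severity is related to deviation from plan.

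**What to change.** **Main change, in Data Analysis.** Before outcome data are examined, name one pre-operative CT measure as severity (version or depth of bone loss) and keep it continuous. For all five groups, add it to the mixed model as a covariate for the first outcome. For the third, add the technology-by-severity interaction. Make clear that this is pre-operative severity. The measure is already collected, so nothing new is recorded. The cost is one parameter for the covariate and 5−1 = 4 for the interaction, assuming a linear relation.

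**Optional addition, in Patient Enrollment.** State whether the new list is stratified. Since envelopes are being made anyway, the statistician could prepare two lists by a severity cut fixed beforehand, in small blocks near the target ratio such as 3:3:3:2:5. Each envelope would be opened only after the CT has been graded, and that order should be written down.

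The downsides should be accepted openly. Some group total misses 20 by three or more in roughly 15 to 27% of runs, although enrolment of up to 120 leaves some room to make up a shortfall. Only the remaining 68 patients can be balanced. Stratifying corrects imbalance but cannot supply severe cases if few are enrolled.

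### Group 5 would be compared partly with patients randomised before it existed, and the analysis model has no term for randomisation period and does not name Group 5

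*Combined protocol and SAP*

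**What the plan says.** **Patient Enrollment.** The target is stated as "Our goal is to have 20 subjects in each treatment group", and "we will enroll up to 120 subjects to control for subject withdrawal after enrollment". When Group 5 was introduced, Groups 1-4 already held 8, 7, 7 and 10 patients; the section gives these as the distribution "at the time that Group 5 was begun is". From then on "new randomization envelopes will be generated that start at number 34", prepared so "that have 12, 13, 13, 10 and 20 in Groups 1-5, respectively". The section acknowledges the new odds: "The change in the odds of being assigned to a particular group will change from 25% previously, to 15 to 19% in Groups 1-4", with 29% in Group 5. The new counts are chosen so that early plus late patients make 20 in each group, so pooling the two periods is intended.

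**Glenoid Instrumentation and Pre-operative planning.** Group 5 (SmartBase) is described as a variation of Group 3, and a rationale is given for testing it in this trial.

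**Data Analysis.** "Average deviations from plan for the four treatment groups will be compared using mixed-effects ANOVA methods". Random effects are added for surgeon. If significant differences are found, all pairs are compared with Holm's procedure. "A significance level of 5% will be used for all testing". There is no term for period, calendar time or envelope list. Nothing restricts Group 5 to concurrent comparators. Group 5 is not named here, nor under Outcome Measures.

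**The concern.** Allocation probabilities differ between the two periods. Randomisation therefore protects comparisons within each period, but not the pooled comparison of group means. The first 32 patients could not have been assigned to Group 5, so for that group they are non-concurrent controls. If placement accuracy drifted over time, part of the drift would appear as an effect of the SmartBase. If accuracy improved, Group 5 would look better than it is.

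The surgeon random effect does not deal with this. It absorbs differences between surgeons, not change over time within a surgeon.

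The documents record no trend, but one is plausible. Detailed Study Design says that two of the three surgeons have extensive experience with the technologies, which leaves room for the third to learn during the trial. The metal-leg IRI is itself a variation on the earlier tool.

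**Working it through.** **1. Inputs (Patient Enrollment).** Before the change: 8, 7, 7, 10, 0 in Groups 1-5. New envelopes: 12, 13, 13, 10, 20. Test level 5% (Data Analysis). The plan gives no SD, effect size or time trend, so the shift d is assumed and expressed in SD units.

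**2. The plan's own figures.**
- 8 + 7 + 7 + 10 = 32 and 12 + 13 + 13 + 10 + 20 = 68. Early plus new is 20 in every group.
- 12/68 = 17.6%, 13/68 = 19.1%, 10/68 = 14.7%, 20/68 = 29.4%. These reproduce the stated 15 to 19% and 29%.
- A list starting at 34 implies 33 earlier numbers against 32 counted patients, so one number is unexplained.

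**3. Bias.** Let f be the share of a group enrolled before the change: 8/20 = 0.40, 7/20 = 0.35, 7/20 = 0.35, 10/20 = 0.50, 0/20 = 0. For a shift d common to all groups, the bias in an unadjusted contrast of groups i and j is (f_i − f_j) × d.

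| Pair | Bias |
|---|---|
| 5 v 1 | 0.40d |
| 5 v 2, 5 v 3 | 0.35d |
| 5 v 4 | 0.50d |
| 4 v 2, 4 v 3 | 0.15d |
| 4 v 1 | 0.10d |
| 1 v 2, 1 v 3 | 0.05d |
| 2 v 3 | 0 |

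**4. False-positive rates.** Simulated with at least 20,000 trials per setting, 20 per group, normal errors with unit SD, no true group effect and no surgeon effect.

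| Test at 5% | d = 0.3 | d = 0.5 | d = 0.8 |
|---|---|---|---|
| Five-group omnibus, no period term | 6% | 7% | 11% |
| 5 v 4 alone, no gate, no Holm | 7% | 11% | 20% |
| 5 v 1 alone, no gate, no Holm | 7% | 9% | 14% |
| 4 v 2 alone, no gate, no Holm | 5% | 5% | 5% |
| Any false pairwise claim after omnibus gate and Holm | 4% | 5% | 8% |
| Four-group omnibus, as Data Analysis is worded | 4.7% | 4.5% | 3.6% |

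The four-group test becomes slightly conservative because the unmodelled shift adds more to the residual variance than it does to the spread of the four group means. With a period term the omnibus and single-pair rates return to about 5% at every d, and any false pairwise claim after gate and Holm occurs in about 3.4% of trials.

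**5. Cost of the period term.** Without it, the SE of any pair is √(1/20 + 1/20) = 0.316 SD. With it, the variance becomes 0.1 + (f_i − f_j)²/S, where S = 20 × Σ f(1 − f) = 20 × (0.24 + 0.2275 + 0.2275 + 0.25 + 0) = 18.9.
- 5 v 1: √(0.1 + 0.16/18.9) = 0.329, up 4.1%.
- 5 v 2 or 3: √(0.1 + 0.1225/18.9) = 0.326, up 3.2%.
- 5 v 4: √(0.1 + 0.25/18.9) = 0.336, up 6.4%.
- 4 v 2 or 3: √(0.1 + 0.0225/18.9) = 0.318, up 0.6%, the largest rise among Groups 1-4.

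Using only patients from envelope 34 on, 5 v 4 has SE √(1/10 + 1/20) = 0.387. This is less precise than the period-adjusted 0.336, but it rests on concurrent randomisation alone.

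**The case against.** The strongest reply is that the written analysis compares four groups and does not mention Group 5. In that analysis the problem is negligible: the omnibus test is not inflated and at most 15% of a shift enters any contrast. This stands as a limit on the point. It does not rescue the plan, because 20 patients are randomised to Group 5 in order to test it, and no other comparison is specified.

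Second, a reader might take 7%, 11% and 20% for 5 v 4 as the trial's false-positive rates. They are not. The plan tests pairs only after a significant omnibus test and then applies Holm, and under that procedure the family-wise rate exceeds 5% materially only at the largest shift tried. That also stands, but Holm does nothing about bias in the estimates.

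Third, the evidence for a trend is thin. Two surgeons are already experienced, and beads had been placed in 66 patients under the IRI and RTI studies. Group 4 repeats an existing protocol, and all surgeons have extensive arthroplasty experience. Learning might therefore be specific to one technology, and an additive period term does not remove a group-by-period effect. This is correct, and it is why the concurrent-only analysis is needed as well.

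Finally, the shares are nominal. Sample Size allows 20-25 per group, and patients in whom the surgeon departs from the assigned technique are excluded.

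**Conclusion.** The point holds for the Group 5 comparisons. They mix concurrent and non-concurrent patients, and 35% to 50% of any common shift between periods passes into them. The size of the shift is assumed, since the documents supply neither a trend nor an SD. The error rates also assume 20 analysed patients per group, normal errors and no surgeon effect.

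Two stronger readings are not supported. A reader might infer that any time trend would be taken wholly as a difference between technologies; at most half of it would be. A reader might also infer that the changed ratios seriously compromise comparisons among Groups 1-4. There the bias is at most 0.15d, and 4 v 2 keeps a false-positive rate of about 5%.

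The omission should be corrected, because the remedy is cheap and the envelope number already identifies the period.

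**What to change.** In Data Analysis (and Outcome Measures):

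1. Name Group 5 as a compared group, so that the model covers all five.
2. Add randomisation period (before v from envelope 34) as a fixed effect beside the surgeon random effects. Take both the omnibus test and the Holm pairwise comparisons from that model.
3. As a sensitivity analysis, repeat each Group 5 comparison using only patients randomised from envelope 34 (nominally 12, 13, 13 and 10 v 20). This also covers technology-specific learning.
4. Account for the one envelope number below 34 that is not among the 32 counted patients, so that period is defined for everyone.

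The cost is a few sentences and one degree of freedom, with no new patients or data. Standard errors rise by 3-6% for Group 5 pairs and by less than 1% for the others.
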